Potential risks to patient participants are considered minimal. For patients in all study arms, there is a potential breach of privacy of individually identifying study data. To minimize this risk, no individually identifying patient information will be made available in publication or dissemination efforts. Results that are shared will be in aggregate form.

For patients whose providers are exposed to the CDS, there are several additional potential risks. First, the CDS may not display all relevant clinical information about the patient, as the CDS is limited to what is contained in the EHR. Second, it is possible that the CDS could erroneously attribute a condition or drug to a patient based on the EHR. In the design phase, the study team will seek and feedback from multiple sources to ensure that the content and CDS firing is as accurate and appropriate as possible. Before implementation, several investigators will review and test the CDS firing to optimize the information displayed. Provider training will inform providers of these limitations and offer strategies to further minimize these risks. Throughout the implementation phase, the study team will request feedback from providers using the CDS to identify any issues and modify the CDS, if needed.

Third, the CDS may be inappropriate for a given individual patient and, if applied without further checking the clinical status of a given patient, could lead to erroneous therapy, adverse events, disability, or death. However, the clinical recommendations are personalized based on the patient's medical problem list, allergies and current medications. The risk of untoward consequences from such clinical actions is considered minimal. Moreover, this potential risk is routinely present in every clinical encounter in the health care system. Fourth, the potential shift in provider prescribing and/or pain management recommendations may also have unintended consequences on patients' post-procedure pain management. It is possible that this shift could cause under-controlled pain. Providers encounter this in current dental practice and will address it in a similar fashion consistent with the reasonable standard of care.

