7 STUDY INTERVENTION DISCONTINUATION AND PARTICIPANT DISCONTINUATION/WITHDRAWAL

7.1 DISCONTINUATION OF STUDY INTERVENTION

Providers should exercise clinical judgment and can at their discretion disregard any information the CDS offers. As such, patients will receive usual dental care, regardless of study arm.

Hospitalizations documented within the HealthPartners electronic health record that occur within a 72-hour window following the index extraction encounter will be chart reviewed for severity and relatedness on a quarterly basis during the intervention period by Co-investigator and/or PI [name]. These hospitalizations rates will be compared at a frequency determined by the DSMB or quarterly whichever is greater.

Based on the relevant data, the study team in consultation with the DSMB would determine whether the study intervention needed to be modified or discontinued.

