8.2 SAFETY AND OTHER ASSESSMENTS

The study does not include objectives or endpoints concerning safety. However, the monitoring activities described below will be conducted to assess possible harm.

Identify whether the CDS inappropriately fires or inappropriately offers considerations

Data source: Provider report to alert study team about potential issues or concerns

Procedures:

1. Providers randomized to an intervention arm will be offered training.

2. They will be instructed to notify the study team when clinical judgement differs from the CDS
3. Notification options: (a) Contact Co-Investigator [name] or PI [name]; (b) select a "feedback" button contained within the CDS

Identify potential adverse events

Data source: HealthPartners electronic health record

Procedures:

1. Gather hospitalizations, emergency department visits, observational bed, and subsequent opioid prescribing made within 3 days post-extraction procedure

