8.3.4 TIME PERIOD AND FREQUENCY FOR EVENT ASSESSMENT AND FOLLOW-UP

Since there are no routine research contacts for all eligible patient participants, we will collect information from the electronic health record about hospitalizations, emergency department visits, observational bed, and subsequent opioid prescribing made within 3 days post-extraction procedure. This is consistent with the usual care delivery pathways and workflows related to dental procedures.

For the sub-sample of patients reached as part of survey data collection, CESR staff provides information to call their dental provider with questions or concerns. In this manner, the study team will not interfere with existing patient-provider communication, but rather support usual care.

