9.4.4 SAFETY ANALYSES

The study does not include objectives or formal endpoints concerning safety. However, potential harm monitoring activities will be conducted as described in section 8.2, and analysis activities conducted as described below.

Identify whether the CDS inappropriately fires or inappropriately offers considerations

The frequency of notifications and content areas (usability, potential safety, or other) will be summarized by study arm (CDE or CDS-E) and provider type.

Identify potential adverse events

Frequencies, proportions and 95% confidence intervals on proportions of patients having hospitalizations documented in the HealthPartners electronic health record within 72-hours of the extraction encounter deemed as adverse events will be summarized by study arm. The

patient encounter study population for H1 and H2 for patients seen following the implementation of the interventions will be used for this analysis. Events with non-overlapping confidence intervals on the proportions by study arm will prompt the study team to assess diagnostic codes related to the encounters from the electronic health record. Frequencies and proportions of diagnostic codes by study arm will be computed.

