10.4 PROTOCOL AMENDMENT HISTORY

Version	Date	Description of Change	Brief Rationale
1.0	07Mar19	Accepted all tracked changes in protocol development and versioned	
2.0	19Dec19	
1.1 Synopsis Study population updated to reflect targeted recruitment numbers
 
1.2 Schema Aligned the wording with the change described above related to permanent tooth extractions
 
4.1 Overall design Study population updated to reflect targeted recruitment numbers
 
8.3.4 Time Period and Frequency for Event Assessment and Follow-Up Includes the visit types described elsewhere.
	Consistency
		5.1. Inclusion criteria Changed molars to permanent teeth	Clinical relevance
		8.2 Safety and other assessments Expands safety-related data collection to more visit types, adding emergency department visits, observational bed, and subsequent opioid prescribing	Alignment with DSMB recommendation
		8.4.2 Unanticipated Problem Reporting Non-serious UPs reporting will not be reported in an expedited fashion, so related text deleted.	Alignment with funder requirements
		9.2 Sample size determination Sample size determination updated to reflect targeted recruitment numbers	Alignment between sample size and targeted recruitment
3.0	10Mar20	1.1 Synopsis	Clarified the study population numbers
		4.1 Overall design	Clarified the study population numbers

		6.1 Study Intervention(s) Administration	Noted the change to access the Prescription Drug Monitoring Program via the electronic health record rather than the clinical decision support
		6.3 Measures to Minimize Bias	Clarified the approach taken to balance provider factors
		9.2 Sample Size Determination	Clarified the study population numbers
		9.3 Populations for Analyses	Clarified the study population numbers
4.0	13Apr20	6.1.1 Study intervention description Timing of change to PDMP access changed to align with HealthPartners Dental Group planning	Due to COVID-19, Epic Care updates at HealthPartners are on hold until further notice.
		8.3.3.2 Relationship to study intervention Added specification to the definition labels	Recommended by Rho/NIDCR in feedback following Site Initiation Teleconference
		8.3.3.3 Expectedness Revised the definition of expectedness	Recommended by Rho/NIDCR in feedback following Site Initiation Teleconference
		8.3.5 Adverse event reporting Referenced further specification about reporting in separate Data and Safety Monitoring Plan	Consistency across protocol and DSMP

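### Section 9.4.4 plans a by-arm result for only one of the four harm events that 8.2 collects; as a lesser point, no supplied analysis uses opioid orders after the extraction day

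*Combined protocol and SAP*

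**What the plan says.** Section 8.2 lists what is gathered to detect possible adverse events: "Gather hospitalizations, emergency department visits, observational bed, and subsequent opioid prescribing made within 3 days post-extraction procedure". Section 8.3.4 repeats the same list and the same 3 days ("we will collect information from the electronic health record about hospitalizations, emergency department visits, observational bed", followed by later opioid prescribing).

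Section 9.4.4 links itself to that list: "potential harm monitoring activities will be conducted as described in section 8.2, and analysis activities conducted as described below". For adverse events it then plans, by study arm, "Frequencies, proportions and 95% confidence intervals on proportions of patients having hospitalizations documented in the HealthPartners electronic health record within 72-hours" of the extraction, restricted to those judged to be adverse events. The next step is a trigger: "Events with non-overlapping confidence intervals on the proportions by study arm will prompt the study team to assess diagnostic codes". Section 7.1 provides for chart review of hospitalizations and adds: "These hospitalizations rates will be compared at a frequency determined by the DSMB or quarterly whichever is greater".

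On opioids, the endpoint table in section 3 and sections 9.1, 9.2 and 9.4.2 all place the H1 outcome on the extraction day or at the index encounter. The opioid part of H2 does the same. Section 8.1 gathers opioid orders within 7 days of the procedure for the primary objective, in both periods. Section 9.4.9 plans no exploratory analyses.

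**The concern.** The interventions aim to move prescribing away from opioids, and section 2.3.1 states the obvious hazard: "It is possible that this shift could cause under-controlled pain". Section 8.3.3.3 lists inadequately managed pain among the expected adverse events. A patient whose pain is not controlled is more likely to show up as a later opioid order or an emergency visit than as an admission. Those are the events that 9.4.4 leaves out. If it is followed as written, the trial reports by arm an event that is a remote sign of the named risk, collects the closer signs, and reports nothing on them.

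The lesser point concerns how H1 will be read. The objective is to decrease opioid prescribing for extractions. In the CDS-E arm, the after-extraction handout is meant in part to help patients decide whether to contact the provider for more help with pain (section 6.1.1). Later orders could therefore differ by arm, and a day-0 result alone cannot separate opioids avoided from opioids postponed.

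**Working it through.** The finding rests on comparing sections of the current text. The plan gives no figure to reproduce.

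**Step 1. Events collected against events analysed**

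| Event within 3 days | Collected (8.2, 8.3.4) | By-arm summary (9.4.4) | Periodic comparison (7.1) |
|---|---|---|---|
| Hospitalization | yes | yes, if judged an adverse event | yes |
| Emergency department visit | yes | none stated | none stated |
| Observation stay | yes | none stated | none stated |
| Subsequent opioid prescribing | yes | none stated | none stated |

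Four types are collected, one is summarised, and 4 − 1 = 3 have no stated by-arm result. The 72 hours in 9.4.4 and the 3 days in 8.2 are the same window and are not part of the gap. Section 9.4.4 also summarises provider notifications about the decision support tool, but that is a separate stream in 8.2 and not one of these four events.

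**Step 2. A possible cause, as context only.** The amendment history for version 2.0 records this change to 8.2: "Expands safety-related data collection to more visit types, adding emergency department visits, observational bed, and subsequent opioid prescribing". The stated reason is a DSMB recommendation. No version lists a matching change to 9.4.4 or 7.1. The mismatch lies between sections of the current text, so it does not depend on this history.

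**Step 3. Opioid windows.** H1 uses day 0. The opioid part of H2 uses day 0. H3 and H4 are survey outcomes. Section 9.4.4 covers hospitalizations. Subgroup and exploratory analyses are marked as not applicable. The number of supplied analyses that use an opioid order after day 0 is zero.

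**Step 4. Why the present trigger should not simply be copied to the other events.** Inputs from the documents: 6,900 intervention-period patients, 51 providers and three arms, so 6,900/3 = 2,300 patients per arm and 6,900/51 = 135.3 per provider. Assumptions, because the documents give no event rates or safety ICC: a 5% event and an ICC of 0, 0.01 or 0.05.

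- Design effect = 1 + (135.3 − 1) × ICC = 1.00, 2.34, 7.71.
- Half-width of one arm's 95% interval = 1.96 × √(0.05 × 0.95 × design effect / 2,300) = 0.89, 1.36, 2.47 percentage points.
- With similar half-widths w in two arms, the separate intervals part only when the difference exceeds 2w = 1.78, 2.73, 4.95 points.
- An interval for the difference itself excludes zero once the difference exceeds √2 × w = 1.26, 1.93, 3.50 points.

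Allowing for clustering is right, but it widens the intervals. A non-overlap rule then becomes harder still to trigger, whereas a rule based on the difference needs a gap about 1.4 times smaller. This bears on the design of the remedy. It does not measure the omission.

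**The case against.** The strongest reply is that the analyses may exist elsewhere. Section 6.3 refers to a Statistical Analysis Plan, section 9.4.1 to a Manual of Procedures, sections 8.3.5 and 8.3.6 to a Data Safety Monitoring Plan, and section 10.1.6 to a DSMB charter that will define the data elements. None of these was supplied. The DSMB is to see safety and efficacy data by arm, and it asked for the three added event types, so it is a natural place to review them. This stands: the gap is established only for the supplied documents. However, DSMB review does not commit the trial to a reported analysis, and 9.4.4 is the section that says it supplies one.

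Second, the protocol says twice that it has no safety objectives or endpoints, and H4 compares pain by arm. Section 9.4.4 nevertheless plans harm analyses, so they should cover what is collected. H4 is descriptive, is expected to rest on about 1,200 survey responders, and measures neither prescribing nor emergency visits.

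Third, the wording is not airtight. The trigger sentence says events in the plural, and 7.1 lets decisions rest on all relevant data. Hospitalization-only is the likelier reading of the trigger, not the only possible one.

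Fourth, on later opioid orders, a data pull wider than the endpoint is not an error. Section 8.1 gives its 7 days no direction and uses the same window for non-opioid recommendations, so it may be no more than a generous linkage window. This also stands, and it is why that point is secondary.

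**Conclusion.** The main point holds: in the supplied text, one of four collected harm events has a planned by-arm result and three have none, including those closest to the risk that the protocol itself names. This is a mismatch between 8.2 and 9.4.4 that should be corrected, and it depends on no assumed rate.

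The secondary point holds in a limited form: no supplied analysis uses opioid orders after the extraction day, so deferral would go unseen. Its size cannot be given, because the documents contain no data on later orders.

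A reader might infer more than this, in three ways that the documents do not support:

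- That the primary endpoint is wrong or has a conflicting window. Its day-0 definition is the same throughout, and H1 is valid for it.
- That prescribing will in fact be deferred. Nothing in the documents shows this; the handout only makes a difference by arm conceivable.
- That harm goes unmonitored, or that no such analysis exists anywhere. There is quarterly chart review of hospitalizations and DSMB review by arm, and four relevant documents were not available.

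**What to change.** 1. Extend 9.4.4 to report all four 8.2 event types by arm over the stated 3 days. Give emergency visits, observation stays and later opioid orders as unadjudicated counts from the record, which avoids new chart review. Present between-arm differences with confidence intervals that allow for provider clustering. Base the prompt for further review on those differences and not on non-overlap of separate intervals. Keep diagnostic-code review for hospital, emergency and observation encounters, since it fits an opioid order poorly.
2. Keep day 0 as the primary endpoint. Beside it, as a supportive analysis, report any opioid order from day 0 through the collected window, using the H1 model and the index provider's arm whoever wrote the order. First confirm that the 7 days in 8.1 run after extraction; if not, use the 3-day data from 8.2, having checked that they are also available for the baseline period, which the pre-to-post contrast needs. State that orders outside the HealthPartners record may be missed and that orders for other indications may be included.
3. If the SAP, Manual of Procedures, Data Safety Monitoring Plan or DSMB charter already contains these analyses, a cross-reference in 9.4 is enough.

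The cost is a few tables and one additional model. The primary endpoint and sample size do not change, and no new collection is needed unless the fallback in item 2 is used and the 3-day data turn out to be missing for the baseline period.

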In addition, patients will receive an educational handout prior to the extraction procedure comparing effectiveness for managing pain, risks and benefits of non-opioid pain medications and opioid medications. This handout intends to initiate a conversation between the patient and provider about patient needs, goals and preferences. The patient will also receive an education handout about pain management after dental extraction for their reference. This handout intends to normalize the experience of some discomfort and to help patients decide about whether to contact their provider for additional help to manage their pain after extraction. Patients will receive usual dental care.

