8 STUDY ASSESSMENTS AND PROCEDURES

8.1 EFFICACY ASSESSMENTS

Primary Objective

To test the efficacy of two interventions (Clinical Decision Support with and without Patient Education), compared to treatment-as-usual to decrease opioid prescribing for dental extractions.

Data source: HealthPartners electronic health record

Procedures:

1. Gather extraction procedure records performed prior to and post CDS implementation
2. Gather opioid medication orders placed within 7 days of extraction procedure
3. Retrieve patient and provider descriptive data

Secondary Objectives

To test the efficacy of two interventions (Clinical Decision Support with and without Patient Education), compared to treatment-as-usual to increase exclusive non-opioid pain management for dental extractions.

Data source: HealthPartners electronic health record

Procedures:

1. Gather extraction procedure records performed prior to and post CDS implementation
2. Gather non-opioid medication recommendations given within 7 days of extraction procedure
3. Gather patient and provider descriptive data

To compare the degree to which each of the 3 study arms (Clinical Decision Support with and without Patient Education, and treatment-as-usual), facilitates shared provider and patient decision-making concerning pain management options for dental extractions.

Data source: Telephone administered patient survey responses

Procedures:

1. CESR staff will administer the survey by telephone
2. CESR staff will input patient responses into RedCap
3. Data will be exported and provided to the statistician

To explore whether the study interventions lead to differences in patient experiences of post-extraction pain. Data source: Patient survey

Procedures:

1. CESR staff will administer the survey by telephone
2. CESR staff will input patient responses into RedCap
3. Data will be exported and provided to the statistician

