9 STATISTICAL CONSIDERATIONS

9.1 STATISTICAL HYPOTHESES

- Primary Efficacy Endpoint(s):

H1 (alternative): Providers in the CDS and CDS-E strategy arms will reduce their likelihood of prescribing opioids for patients following extractions more than providers in the SP arm.

H1 endpoint: Comparison across study arms of the differential change in percentage of permanent tooth extraction encounters having an associated opioid prescription on the day of the extraction encounter, from the one year prior to the intervention implementation to one year after the intervention implementation.

- Secondary Efficacy Endpoint(s):

H2 (alternative): Providers in the CDS and CDS-E strategy arms will increase their likelihood of prescribing or recommending non-opioid analgesics at the extraction encounter and not prescribing opioids for patients following extractions more than providers in the SP arm.

H2 endpoint: Comparison across study arms of the differential change in percentage of permanent tooth extraction encounters having both 1) a prescription or recommendation in the treatment plan for non-opioid analgesics and 2) to not have an associated opioid prescription on the day of the extraction encounter, from the one year prior to the intervention implementation to one year after the intervention implementation.

H3 (alternative): Patients will report higher levels of the extent of shared decision making in the CDS-E arm than the CDS or SP arms.

H3 endpoint: Comparison across study arms of the mean of the 3-item composite of adapted Collaborate Shared Decision Making score reported by the patient.

H4 (descriptive): Compare patient report of average pain in the week following extraction across the 3 study arms.

H4 endpoint: Comparison across study arms of the mean pain rating in the 3-6 days since the extraction encounter, self-reported by patients.

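### Section 8.2 collects four kinds of possible harm event, but 9.4.4 specifies a by-arm summary for hospitalizations only, so opioids first prescribed on days 1 to 3 enter no specified analysis

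*Combined protocol and SAP*

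**What the plan says.** The data collection is broad. Under the item on potential adverse events, protocol section 8.2 instructs staff to "Gather hospitalizations, emergency department visits, observational bed, and subsequent opioid prescribing made within 3 days post-extraction procedure". Section 8.3.4 repeats the list and takes it from the electronic health record for all eligible patients.

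The analysis is narrower. Section 9.4.4 opens by saying that "potential harm monitoring activities will be conducted as described in section 8.2, and analysis activities conducted as described below". Under the matching item it provides frequencies, proportions and 95% confidence intervals, and the text is that "hospitalizations documented in the HealthPartners electronic health record within 72-hours of the extraction encounter deemed as adverse events will be summarized by study arm". Section 7.1, on review during the trial, is limited in the same way: "These hospitalizations rates will be compared at a frequency determined by the DSMB or quarterly whichever is greater".

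On prescribing, section 8.1 has staff "Gather opioid medication orders placed within 7 days of extraction procedure", but the H1 endpoint in section 9.1 counts encounters "having an associated opioid prescription on the day of the extraction encounter". H2 uses the same day for its no-opioid component. On risk, section 2.3.1 says of the change in prescribing: "It is possible that this shift could cause under-controlled pain". Section 8.3.3.3 lists inadequately managed pain among the expected adverse events.

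**The concern.** The intervention is meant to reduce opioid prescribing at the extraction visit. The obvious question for a reader of the results is how much prescribing was avoided and how much was only delayed. A patient sent home without an opioid who is given one on day 2 counts as a success for the no-opioid part of H1 and H2. If that patient is not hospitalized, nothing in 9.4.4 picks up the event. Emergency department visits and observation stays, which might also reflect pain that was not controlled, are likewise collected with no stated summary.

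If the plan is followed exactly, the trial could report a reduction in same-day prescribing without saying how many patients received an opioid in the next 3 days, although 8.2 collects that information for everyone. Leaving the summaries unspecified also leaves their reporting to a later choice.

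**Working it through.** **Step 1: trace each event kind through the plan.** Day 0 is the day of extraction.

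| Event within 3 days | Collected (8.2, 8.3.4) | Compared during the trial (7.1) | By-arm analysis (9.4.4) | Part of an H1 to H4 endpoint |
|---|---|---|---|---|
| Hospitalization | yes | yes | yes, if deemed an adverse event | no |
| Emergency department visit | yes | not stated | not stated | no |
| Observation stay | yes | not stated | not stated | no |
| Opioid prescribed after day 0 | yes | not stated | not stated | no; H1 and H2 stop at day 0 |

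One of the four has a specified by-arm analysis and three have none. The other by-arm item in 9.4.4 concerns provider notifications about the decision support tool, which is not one of these events. Sections 9.4.7 (subgroups) and 9.4.9 (exploratory analyses) are marked not applicable, so they do not fill the gap.

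**Step 2: what H4 covers.** Section 9.2 gives 1,520 patients approached and a 79% response: 1,520 × 0.79 = 1,200.8, which agrees with the stated 1,200. That is about 400 per arm, and 1,200 / 6,900 = 17% of the target intervention-period patients. H4 estimates mean pain by arm in this group and counts no prescriptions or visits.

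**Step 3: scale.** Inputs from sections 4.1 and 9.2: 6,900 target patients in the intervention period, 1:1:1 allocation, opioid prescribing falling from 40% to 15% in an intervention arm and from 40% to 38% under standard practice.

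- Patients per arm: 6,900 / 3 = 2,300, taking equal patient numbers per arm.
- Detectable differential reduction: (40 − 15) − (40 − 38) = 23 points, as stated in 9.2.
- Fewer same-day prescriptions per intervention arm at that difference: 0.23 × 2,300 = 529.
- If a share *s* of those patients receives an opioid on days 1 to 3, the number is 529 × *s*, or 23 × *s* points.

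| Assumed share *s* | Patients per arm | Points |
|---|---|---|
| 5% | 26 | 1.15 |
| 10% | 53 | 2.3 |
| 20% | 106 | 4.6 |

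The documents give no value for *s*; the three shares are assumptions that show a range.

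**The case against.** The strongest reply is that these items are for monitoring and were never meant for a trial analysis. Sections 8.2 and 9.4.4 both say that the study has no formal safety endpoints. The amendment log attributes the wider event list to a DSMB recommendation. Under section 10.1.6 the DSMB reviews safety data for each arm at least semiannually, with its data elements defined when the charter is written. Sections 8.3.5 and 8.3.6 refer to a separate Data Safety Monitoring Plan for reporting details. A reader might infer from 9.4.4 that nobody will see emergency visits or later prescribing by arm. The documents do not support that: the charter and the monitoring plan are not supplied and may well tabulate them. What can be said is that the protocol states no such analysis. Having no formal endpoint also does not explain why one of the four kinds is analysed and three are not.

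The second reply is H4. A reader might infer that under-controlled pain is examined only through hospitalizations. That is wrong: H4 compares patient-reported pain by arm, with a random intercept for provider, and is a more direct measure than a later prescription. It stands as a real safeguard, but it is descriptive, limited to survey completers, and cannot show how much prescribing was delayed.

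Third, the follow-up rule in 9.4.4 speaks of events in general when confidence intervals do not overlap. It comes straight after the hospitalization proportions and names no other kind, so it cannot be relied on to cover the rest.

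Finally, the 23 points are the difference the design can detect with 80% power. They are not a planned or expected result, and the patient counts above are for scale only.

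**Conclusion.** The point holds as a minor mismatch between what is collected and what is analysed. Three of the four event kinds in 8.2 have no by-arm summary in the protocol, and an opioid first prescribed on days 1 to 3 is scored as no opioid in H1 and H2 and enters no other specified analysis. At the detectable difference, each 10% of avoided same-day prescriptions that reappears within 3 days is about 53 patients per arm, or 2.3 points. This rests on the target of 6,900 patients, equal arms and an assumed share.

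It would go too far to say that H1 is biased: its endpoint is defined as same-day prescribing and the analysis answers that question. Nor do the documents allow a claim about how precisely a difference in later prescribing would be estimated, because they give neither a rate nor an intracluster correlation for these events.

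**What to change.** In 9.4.4, under potential adverse events, name all four event kinds from 8.2 and extend the existing summary to each: counts, proportions and 95% confidence intervals by arm, preferably allowing for clustering by provider. Label the summaries descriptive. Report later opioid prescribing beside the H1 result, separating patients with no opioid on day 0 from those receiving a repeat prescription, so that delayed and continued prescribing are not mixed.

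The cost is a few lines of text and one table from data that 8.2 already collects, with no new patients or tests. The drawback is interpretation. A later prescription is an indirect sign: it may be appropriate rescue, and orders outside the HealthPartners record are not seen. In CDS-E the post-extraction handout is itself intended to "help patients decide about whether to contact their provider for additional help to manage their pain after extraction", which could raise later prescribing without worse pain. The plan should state these limits next to the table and have it read together with H4.
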